#### **4.7.1.1 Discontinuation from Study Drug**

In addition to the criteria listed above, reasons for withdrawal of the study drug but which do not preclude the patient remaining in the study include, but are not limited to, if the patient:

- Meets the discontinuation criteria in the risk mitigation and dose modification strategy (see Section 5.1).
- Misses three consecutive doses of study drug on scheduled visits in the double-blind period.
- Experiences two relapses in the *OLE* period with a more severe intensity compared with the last relapse prior to baseline.

The Investigator should consult with the Medical Monitor if these relapses meet this criterion.

- Experiences malignancy or a severe allergic or anaphylactic reaction to satralizumab.
- Pregnancy.
- Unacceptable toxicity.

If the patient is unwilling to continue in the study, he/she will be asked to return to the clinic for a Withdrawal visit (see Section 4.5.2.3) and may undergo follow-up assessments (see Section 4.5.2.4). The primary reason for premature study drug discontinuation should be documented on the appropriate eCRF. Patients who discontinue study drug prematurely will not be replaced.

#### **4.7.1.2 Withdrawal from Study**

Every effort should be made to obtain information on patients who withdraw from the study. The primary reason for withdrawal from the study should be documented on the appropriate eCRF. Patients will not be followed for any reason after consent has been withdrawn. Patients who withdraw from the study will not be replaced.

#### **4.7.2 Study and Site Discontinuation**

The Sponsor has the right to terminate this study at any time. Reasons for terminating the study may include, but are not limited to, the following:

- The incidence or severity of AEs in this or other studies indicates a potential health hazard to patients
- Patient enrollment is unsatisfactory

The Sponsor or its designee will notify the Investigator if the study is placed on hold, or if the Sponsor decides to discontinue the study or development program.

The Sponsor has the right to discontinue a site at any time. Reasons for discontinuing a site may include, but are not limited to, the following:

- Excessively slow recruitment
- Poor protocol adherence
- Inaccurate or incomplete data recording
- Non-compliance with the International Conference on Harmonisation (ICH) guideline for GCP.

#### **4.8 ADOLESCENTS**

Adolescents (i.e., patients from 12 to 17 years old with NMO/NMOSD) will be randomized into the double-blind period of the study as well as adults. Recruitment of adolescents into the double-blind period of the study will be according to Section 3.1.2. After the total number of protocol-defined relapses judged by the CEC reaches 26, the recruitment period for the adolescents may be continued in the extension period until a minimum of 8 adolescents are enrolled into the study.

The overall study objectives remain the same and include adolescents enrolled into the double-blind period of the study. The objective and endpoints for adolescents are as follows:

##### **Specific Objective for the Group of Adolescents**

The objective for adolescents who are enrolled into this study (double-blind period or extension period) is as follows:

- To evaluate the safety, tolerability, efficacy, PK, PD and immunogenicity of satralizumab in adolescents.

## **Specific Outcome Measures (Endpoints) for the Group of Adolescents**

### **Primary Outcome Measures (Endpoints)**

- Safety assessments
  - Incidence and severity of AEs, AESIs, SAE and selected AEs
  - Vital signs (temperature, systolic and diastolic blood pressure and pulse rate), physical examinations, clinical laboratory tests (hematology, chemistry and urinalysis), 12 lead ECGs, suicidality (C-SSRS)
- PK, PD and immunogenicity

### **Secondary Outcome Measures (Endpoints)**

- TFR
- ARR
- Change in EDSS score
- Change in visual acuity (Snellen chart)
- Change in SF-36 score
- Change in VAS score for pain
- Change in FACIT Fatigue score
- Change in EQ-5D score
- Change in mRS score
- Change in ZBI score

The inclusion criteria and exclusion criteria for adolescents who will be enrolled into the double-blind period are shown in Section 4.1. For adolescents who may be enrolled after the end of the double-blind period, the inclusion criterion 2 and the annotation “\*” in the exclusion criterion 20 are as follows (other criteria are same). Baseline of the extension period will occur after the screening period. Screening tests and evaluations will be performed within 28 days prior to baseline, unless otherwise specified. All screening evaluations must be completed and reviewed to confirm that patient meets all eligibility criteria before the first study drug administration.

### **Inclusion Criterion 2**

Clinical evidence of at least 2 documented relapses (including first attack) prior to screening.

## **The annotation “\*” in the exclusion criterion 20**

\* If retest is conducted, the last value of retest before baseline must meet study criteria.

## **5. ASSESSMENT OF SAFETY**

### **5.1 SAFETY PLAN**

#### **5.1.1 Important Identified and Potential Risks of Satralizumab**

On the basis of mechanism of action, key non-clinical and clinical safety findings, experience with similar molecules, an Integrated Summary of Safety Information is included in the current Investigator’s Brochure for satralizumab. *Please refer to the current satralizumab Investigator’s Brochure for an up-to-date summary of available safety information.*

*There have been no important identified or potential risks for satralizumab. The safety management plan for other potential risks and laboratory abnormalities associated with satralizumab, and risks for drugs in the same drug class are outlined below.*

- Serious Infections
- Neutropenia and Potential Risk of Infection
- Thrombocytopenia and Potential Risk of Bleeding
- Liver Enzyme and Bilirubin Elevations and Potential Risk of Hepatotoxicity
- Elevated Lipid Levels and Potential Risk of Cardiovascular/Cerebrovascular Events
- Immunogenicity
- Serious Hypersensitivity Reactions
- CYP450 Enzyme Normalization
- Complications of Diverticulitis
- Malignancies
- Demyelinating Disorders

In order to address the identified and potential risks for the patients, the following safety precautions are included in the study design:

- In addition to regular standard safety evaluations (laboratory measures, physical examinations, vital signs and ECG), a special focus will be placed on the above risks.

- An IDMC will periodically evaluate the safety of patients every six months *during the double-blind period of the study*.
- Dear Doctor Letters should be provided to the patient about the study and the investigational drug. Patients should be instructed to inform about this study and the investigational drug to healthcare professionals in case they contact any other hospital/clinic, etc.

Recommendation for vigilance with regards to sign and symptoms of particular safety events are summarized in the following sections.

#### **5.1.1.1 Serious Infection**

In a Phase 1 multiple dose study of satralizumab in patients with RA (SA-105JP), one case of serious infection, bronchopneumonia (1 of 33 patients), was reported. Serious infection is an identified risk of tocilizumab. In the all-exposure population of tocilizumab, the most common serious infections included pneumonia, urinary tract infection, cellulitis, herpes zoster, gastroenteritis, diverticulitis, sepsis and bacterial arthritis.

Treatment with satralizumab suppresses acute phase reactions (fever, increase in CRP, etc.) induced by IL-6 and accordingly suppresses signs and symptoms associated with infection, which may delay the detection of infections. As a result, it may potentially make the infection more *severe*.

Patients with an active infection (excluding fungal infections of nail beds or caries dentium) within 4 weeks prior to baseline will be excluded from this study.

Patients with evidence of active TB (excluding patients receiving chemoprophylaxis for latent TB infection) will be excluded from this study.

Patients with chronic active hepatitis B or C will be excluded from this study.

Patients who received any live or live attenuated vaccine within 6 weeks prior to baseline will be excluded from this study.

- Satralizumab should not be initiated or administered in patients with active infections.
- Patients should be closely monitored for the development of signs and symptoms of infection, as signs and symptoms of acute inflammation may be lessened due to suppression of the acute phase reactants.

- Patients must be instructed to contact their physician immediately when any symptoms suggesting infection appear, in order to *ensure* rapid evaluation and appropriate treatment.
- If a patient develops a serious infection, administration of satralizumab is to be interrupted until the infection is resolved. The *treating physician* should *conduct a benefit-risk assessment* before resuming treatment with satralizumab.
- Live or live attenuated vaccines should not to be given within 6 weeks prior to baseline and during the course of the study as clinical safety has not been established.

For patients with NMO participating in this protocol, therapies used to treat NMO (corticosteroids, azathioprine, mycophenolate mofetil) have been shown to be associated with infections, particularly serious infections.

#### **5.1.1.2 Neutropenia and Potential Risk of Infection**

Reversible neutropenia was reported in 1 of 33 patients with RA in Phase 1 multiple dose study (SA-105JP).

*In the completed double-blind period of the Phase 3 studies, decreases in neutrophil counts have occurred following treatment with satralizumab, which was not associated with serious infections. The majority of neutrophil decreases were transient or intermittent.*

Neutropenia has been observed during administration of tocilizumab. Infections have been uncommonly reported in association with treatment-related neutropenia in long-term extension studies and postmarketing clinical experience.

Patients with a low neutrophil count  $<2 \times 10^3/\mu\text{L}$  will be excluded from this study.

Caution should be exercised in patients with a low neutrophil count and appropriate measures (such as interruption of satralizumab) should be considered if neutropenia persists.

Recommended dose interruption based on ANC results is shown in [Table 2](#).

**Table 2: Neutropenia Risk Mitigation**

ANC (/μL)	Action
>1,000	Maintain dose
500 – 1,000	
 
• If neutropenia persists, satralizumab should be interrupted until ANC is above 1,000/μL.
 
• If ANC was under 1,000/μL at the previous laboratory test, ANC must be checked before treatment with the satralizumab (e.g., ANC test at site).
 

<500	Satralizumab should be discontinued.

ANC = absolute neutrophil count.

### 5.1.1.3 Thrombocytopenia and Potential Risk of Bleeding

Treatment-related reduction in platelet count was observed in Phase 1 multiple-dose study with RA (SA-105JP), although these were within normal range.

*In the Phase 3 studies, decreases in platelet counts have been observed following treatment with satralizumab.*

Treatment-related reduction in platelets was not associated with bleeding events in clinical trials.

Patients with a platelet count below  $10 \times 10^4/\mu\text{L}$  will be excluded from this study.

Caution should be exercised in patients with a low platelet count and appropriate measures (such as interruption of satralizumab) should be considered if thrombocytopenia persists.

Recommended dose interruption based on platelet counts are shown in [Table 3](#).

**Table 3: Thrombocytopenia Risk Mitigation**

Platelet count (/μL)	Action
>75,000	Maintain dose
50,000 – 75,000	If thrombocytopenia persists, satralizumab should be interrupted until platelet count is above 75,000/μL.
<50,000	Satralizumab should be discontinued.

#### 5.1.1.4 Liver Enzyme and Bilirubin Elevations and Potential Risk of Hepatotoxicity

Reversible elevations of AST and total bilirubin were each observed in 2 healthy subjects and reversible elevation of ALT in 1 healthy subject out of 72 healthy subjects in the Phase 1 single ascending dose study (SA-001JP).

*In the Phase 3 studies, mild and moderate elevations of liver transaminases have been observed with satralizumab treatment. Most elevations were  $<5 \times$  ULN and resolved while on treatment with satralizumab. Elevations of ALT or AST  $>3 \times$  ULN were not associated with increases in total bilirubin.*

It has been reported that IL-6 appears to have a hepatoprotective effect on various forms of liver injury and promotes hepatocyte regeneration. Patients with elevated transaminases ALT or AST  $>1.5x$  ULN will be excluded from this study.

Liver function markers should be closely monitored when satralizumab is administered, especially concomitantly with hepatotoxic drugs or administered in patients with elevated transaminases.

Recommended dose interruptions based on transaminases are shown in [Table 4](#).

**Table 4: Hepatic Enzyme Risk Mitigation**

AST or ALT values	Action
$>1$ to $3x$ ULN*	

Reduction (if necessary, interruption) of hepatotoxic drugs could be considered.

For persistent increases in this range, satralizumab could be interrupted until AST and ALT is below ULN*.

$>3$ to $5x$ ULN	Laboratory tests (ALT, AST, ALP and TBL) should be repeated within 72 hours to confirm value. The presence of clinical symptoms should be queried. Patients who are far away from the trial site may be retested locally if prompt return to the trial site is difficult. If close monitoring is not possible, the drug should be discontinued. satralizumab should be interrupted until AST and ALT is below $3x$ ULN. If at least one of following associated, satralizumab should be discontinued: 

Total bilirubin <math>>2x</math> ULN and/or

INR <math>>1.5x</math> ULN and/or

Appearance of fatigue, nausea, vomiting, right upper quadrant pain or tenderness, fever, rash, and/or eosinophilia

AST or ALT values	Action
>5x ULN	
Laboratory tests (ALT, AST, ALP, and TBL) should be repeated within 72 hours as soon as possible to confirm value. If continued, satralizumab should be discontinued immediately and gastroenterology expert should be contacted.
 
The presence of clinical symptoms should be queried. Patients who are far away from the trial site may be retested locally if prompt return to the trial site is difficult.

ALP=alkaline phosphatase; ALT=alanine aminotransferase; AST=aspartate aminotransferase; INR=international normalized ratio; TBL=total bilirubin; ULN=upper limit of normal.

\* ULN or patient's baseline whichever is higher.

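### In Table 4 the >5x ULN row lacks the hold, the no-monitoring default and the associated-findings stop that the milder >3 to 5x row contains

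*Protocol*

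**What the plan says.** Section 5.1.1.4 presents Table 4 as advice on dosing: "Recommended dose interruptions based on transaminases are shown in" the table. Section 4.7.1.1 sends sites back to Section 5.1 for the criteria for stopping study drug, so this table is the operative liver rule.

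The >3 to 5x ULN row asks for a repeat within 72 hours. It adds a default, "If close monitoring is not possible, the drug should be discontinued", and a hold, "satralizumab should be interrupted until AST and ALT is below" 3x ULN. It directs discontinuation if total bilirubin exceeds 2x ULN, INR exceeds 1.5x ULN, or one of a list of symptoms appears.

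The >5x ULN row also asks for a repeat within 72 hours to confirm the value. Its one drug action is then conditional: "If continued, satralizumab should be discontinued immediately and gastroenterology expert should be contacted". It goes on to say "The presence of clinical symptoms should be queried", with no action attached to the answer, and it allows a local retest for patients far from the site. It does not say what to do while the repeat is pending, or if no repeat is obtained.

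**The concern.** A dose-modification table is expected to become more cautious as the laboratory value worsens. Once a value above 5x is confirmed, this one does. On a first, unconfirmed value it does not: a site following the text finds fewer instructions for a patient at 6x ULN than for one at 4x. At 4x, a patient who cannot be monitored stops drug; at 6x, the text is silent. At 4x with bilirubin above 2x ULN, drug stops; at 6x with the same bilirubin, nothing is directed unless the repeat shows that the elevation has continued.

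What is at stake is the safety of individual patients in the open-label extension, where Version 11 widens dosing away from the site and blood tests are less frequent than injections.

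**Working it through.** The plan gives no figure to reproduce. The check sets the two rows side by side, looks for the missing action elsewhere, and then counts the doses involved.

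**Row comparison (Protocol Table 4)**

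| Situation | >3 to 5x ULN | >5x ULN |
|---|---|---|
| Interruption | directed, until below 3x ULN | none written |
| Close monitoring not possible | discontinue | none written |
| Bilirubin >2x ULN, INR >1.5x ULN or listed symptom | discontinue | none written; symptoms only queried |
| Value confirmed on repeat | interruption continues | discontinue at once, contact expert |

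**Which repeat results leave a gap after a first value above 5x**

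- Repeat still above 5x: discontinue. No gap.
- Repeat at >3 to 5x: the lower row applies, with its hold, default and stop rule. No gap.
- Repeat at 3x ULN or below: the lowest row applies, which only permits a hold for persistent rises. If bilirubin, INR or symptom findings came with the first value, no drug action is directed on them. Gap. It needs a fall of more than (5 − 3)/5 = 40% between the two draws.
- No repeat obtained: no drug action is directed. Gap.

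**Other sections.** Section 4.7.1 gives the investigator, Sponsor and Medical Monitor general discretion to stop drug. Section 4.7.1.1 points back to Section 5.1. Section 5.1.1.4 asks for close monitoring of liver markers. Section 5.3.5.6 requires reporting within 24 hours of ALT or AST >3x ULN with bilirubin >2x ULN or jaundice. None of these sets a hepatic dosing action.

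**Doses before the retest is due.** Inputs: dosing at Weeks 0, 2 and 4, then every 4 weeks (Section 4.3.2.2); retest within 72 hours, that is 3 days. For a draw on a dosing day at nominal intervals, the first result would have to take longer than the following before the retest window reached the next dose:

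- Weeks 0 to 4: 14 − 3 = 11 days
- every-4-weeks dosing: 28 − 3 = 25 days

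The wait for a retest will therefore seldom meet a dose.

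**Doses if the retest is never done.** Inputs: Table 7 schedules laboratory tests every 4 weeks with dosing up to Week 48 of the extension, and every 12 weeks thereafter with dosing still every 4 weeks. Doses strictly between scheduled draws = (laboratory interval / dose interval) − 1:

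- Week 4 to Week 48: 4/4 − 1 = 0
- after Week 48: 12/4 − 1 = 2. Example: draw at Week 60, doses at Weeks 64 and 68, next draw at Week 72.

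Chemistry goes to a central laboratory (Section 4.5.1.11), so the dose at the next draw visit may be given before its result is back. That adds one: 0 + 1 = 1 up to Week 48, and 2 + 1 = 3 after it.

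**The case against.** The strongest objection concerns the contrast before the retest. The >3 to 5x row also opens with a repeat to confirm the value, and its interruption comes later in the cell, so the hold can be read as following confirmation. On that reading neither row acts on a first value. This stands: the contrast while a repeat is pending is uncertain, and it rarely reaches a dose. It does not touch the no-monitoring default or the associated-findings stop, which the >5x row lacks on either reading.

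A second objection is that confirming before acting is normal in this section. A reader might infer from the lowest ANC row of Table 2, "Satralizumab should be discontinued", and its counterpart for platelets in Table 3 that the protocol always acts on a severe value itself. The tables do not support so general a rule, because their middle rows depend on persistence. Confirming a >5x value is a legitimate design choice; the point is only that nothing is written for when confirmation fails to arrive.

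Third, a patient above 5x is also above 3x and might inherit the lower row's actions. But that row's heading stops at 5x, the table does not call its rows cumulative, and the >5x row repeats the retest, symptom and local-retest instructions as though complete in itself.

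Fourth, a missed retest followed by further dosing is largely non-adherence, and sites may stop drug on judgment. That limits the weight. However, Table 7 itself foresees local testing only where possible in emergencies after Week 48, and Section 4.3.2.2 allows off-site dosing on days without on-site assessments, so a missed test is not far-fetched.

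**Conclusion.** The point holds as a cheap patient-safety improvement, minor in weight. The >5x row omits three protections that the row below it has. This leaves two situations without a directed drug action: a retest not obtained, and a repeat at 3x ULN or below after a first value with bilirubin, INR or symptom findings.

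A reader might infer that patients above 5x are treated more leniently overall, or that the trial's findings are affected. Neither is supported. A confirmed value above 5x leads to immediate discontinuation and expert contact. Section 1.3 states that the double-blind period is complete, so a change can reach only the extension, whose dosing ends by 31 December 2021.

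The worst case is two doses after Week 48 before the next scheduled draw, or three if that visit's result is late. It assumes nominal visit timing, a missed retest, and doses still given. The number of patients in either situation is not stated. Section 5.1.1.4 reports that most Phase 3 elevations were below 5x ULN and that values above 3x ULN were not associated with bilirubin increases, so few are expected.

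**What to change.** Add to the >5x ULN row of Table 4: *Interrupt satralizumab pending the repeat; discontinue if the repeat or close monitoring is not possible; discontinue if total bilirubin >2x ULN, INR >1.5x ULN or a listed symptom is associated, as in the >3 to 5x row.* Keep immediate discontinuation and expert contact for a confirmed value above 5x.

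This rewords one table cell, by amendment or site letter. It needs no new tests, since bilirubin and INR are already in the scheduled laboratory panel (Section 4.5.1.11). The downside is an occasional dose delayed, or drug stopped, on a value that would not have been confirmed. That cost is real: fatigue is on the symptom list and common in this disease (Section 1.1.1), and Section 3.2.3 describes any relapse as potentially catastrophic. The >3 to 5x row already accepts the same cost at a lower enzyme level. If the sponsor thinks a stop on symptoms alone is too strict, both rows should be softened together.

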#### 5.1.1.5 Elevated Lipid Levels and Potential Risk of Cardiovascular/Cerebrovascular Events

Slight increases in lipid levels (3 AEs of hyperlipidaemia [mild]) were observed in 3 out of 33 patients in Phase 1 multiple dose study (SA-105JP), *while no cardiovascular/cerebrovascular events have been observed in Phase 1 trials of satralizumab. Increases in total cholesterol, LDL cholesterol, HDL cholesterol and triglycerides due to administration of tocilizumab have been observed. However, it is unknown whether these changes were associated with cardiovascular events.*

*In the Phase 3 studies, elevations in total cholesterol and triglycerides were observed. The elevations in lipid parameters did not require dose interruption. Patients should be managed according to the guideline such as the National Cholesterol Education Program Adult Treatment Panel III or Japan Atherosclerosis Society guideline or other guideline.*

